Clinic personnel will complete a formative evaluation at 0-, 6-, 12- and 24- months of the study, receiving a survey to assess *acceptability, appropriateness, feasibility, success, and permanence of the DA*. This survey will be administered to up to 15 clinic personnel per site at most and will last for 10 minutes. Clinic personnel will receive an email with a link to complete the online Qualtrics survey. Reminder emails will be sent to non-responders 1- and 2-weeks after the initial survey email. All outcome will be measured on a Likert-type scale from (strongly agree = 1) to (strongly agree = 5). For composite outcomes, mean scale scores will be computed.

Specific Aim 3: Semi-structured interviews will be administered to the clinic personnel interviewed as part of Specific Aim 1, as well as 2 patient participants per site from Specific Aim 2, over the phone to reduce patient/clinic personnel burden. The interviews will be done by the UAB study team lead by [name], in collaboration with Drs. [name] and Qu, coordinated by [name] and [name]. These interviews will be conducted within 45-60 minutes and transcribed to

analyze the effectiveness of implementing the decision aid in a normal clinic setting and sustainability facilitators and barriers. These responses will develop the step-by-step implementation guide for future use in a clinic setting.

The study team will take into consideration the following while developing the interview guide for Specific Aim 3:

- Turnover in clinic personnel*
 - There may be turnover in clinic personnel whom were interviewed for Specific Aim 1. There will be specific questions in the interview guide for Specific Aim 2 to account for this.

Study coordinators will be interviewed every six months to assess the implementation and sustainability of the DA in the clinic flow. This survey will be given over the phone to one study coordinator per site every 6 months, lasting no more than 30 minutes per site. These interviews will be recorded and transcribed for study records; any actionable concerns will be decided upon in the following weekly study conference call.

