9.2 Sample Size Determination

A power analysis for the quantitative portion of Specific Aim 2 was conducted using the following assumptions: (1) 16 clinics and (2) an intraclass correlation coefficient of 0.05. This provided us with a total confidence interval width of 5.3% for 10% of the total clinic population that is administered the lupus DA to a width of 8.1% , if 40% patients are administered the lupus DA. For outcomes on a 5-point Likert scale, the corresponding 95% CI widths for standard deviation of 0.5 and 2.0 on the mean score is estimated to be 0.09 vs. 0.35, respectively. For individual-level outcomes measured as a rate (e.g., # visits/1,000) or as means (e.g., Likert-scale), we anticipate small margins of error. A minimum number of proposed sites (n=16) are needed to comprehensively assess how different implementation strategies are influenced by and interact with different contextual conditions (different geographic areas, clinic type, and patient diversity) to affect implementation effectiveness, and thus, determine the generalizability of the study findings. However, given the proven effectiveness of the DA (original PCORI study), and in the spirit of dissemination and implementation research, we will continue to recruit to our proposed maximum sample size target of 3,000.

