9.4.2 Analysis of the Primary Efficacy Endpoint(S)

Specific Aim 1:

Qualitative: Emergent theme analysis, within each clinic and based on the CFIR domains, will be initially conducted. These themes will be used to identify the preferred implementation strategies for use in a clinic. These within-case themes also will be used to compare and contrast between clinics to identify unique and common barriers to implementation.

Quantitative: Univariate statistics (means, standard deviations) will be used to describe each clinic's learning environment and readiness to implement change. Spearman correlations will be estimated to assess how different aspects of the clinic's learning environment and readiness to implement change may vary across clinics. Similarly, t-tests and one-way ANOVAs will be estimated to assess how the learning environment and readiness to change varies a

function of clinic characteristics (e.g., location, private vs. academic). Penetration will be assessed by evaluating the proportion of eligible patients reviewing the DA overall and in each site. Simple proportions and 95% confidence intervals will be computed. Patient healthcare utilization outcomes (e.g., inpatient visits and ER/urgent care visits) will be assessed similarly.

The results of the qualitative and quantitative analyses described above will be consolidated to construct a profile or “case study” for each clinic.

Specific Aim 2:

Targeted participants for this aim are (1) age \geq 18 years with a diagnosis of lupus from participating clinics. Objective measures will be assessed in both clinic personnel and in patients. Clinical personnel will evaluate perceived acceptability of intervention measure for the DA, perceived DA implementation success, and perceived DA permanence. All will be assessed on an ordinal scale (strongly disagree = 1) to (strongly agree = 5). Similarly, patients will evaluate perception of DA usefulness, patient satisfaction for the DA, perceived intervention appropriateness measure for the DA, and perceived feasibility of intervention measure for the DA. All of these patient assessments will be measured on a Likert-type scale.

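### The Likert confidence interval widths in section 9.2 (0.09 and 0.35) cannot be reached at one wave by at most 240 staff, nor by patients under the plan's own 16 clinics and ICC of 0.05

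*Combined protocol and SAP*

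**What the plan says.** Section 9.2 opens with "A power analysis for the quantitative portion of Specific Aim 2 was conducted" and lists its assumptions as "1) 16 clinics and (2) an intraclass correlation coefficient of 0.05". It first gives widths for the proportion of patients given the decision aid, starting with a "total confidence interval width of 5.3" per cent. It then turns to scores: "For outcomes on a 5-point Likert scale, the corresponding 95% CI widths for standard deviation of 0.5 and 2.0 on the mean score" are put at 0.09 and 0.35. No number of respondents is attached to any of these figures.

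The Aim 2 scores come from two groups. Section 9.4.2 says "Clinical personnel will evaluate perceived acceptability of intervention measure for the DA, perceived DA implementation success, and perceived DA permanence", scored 1 to 5, and then names four outcomes rated by patients. Section 9.3 puts staff who complete the online surveys in the Aim 2 analysis population. On the number of staff, section 6.1 says "This survey will be administered to up to 15 clinic personnel per site at most"; the survey is repeated at 0, 6, 12 and 24 months. For patients, section 8 expects at least 35 per site and section 9.2 sets a maximum of 3,000.

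**The concern.** One pair of widths is offered for all 5-point Likert outcomes of Aim 2, although the two groups of raters differ greatly in size. The staff group has a fixed ceiling, and recruiting more patients does nothing for it. The widths also look too narrow for any group once the ICC in the same section is applied.

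What is at stake is what a reader of the plan expects. Staff perceptions are a named part of the Aim 2 evaluation, and section 9.1 intends to compare trajectories between groups of sites defined by implementation strategy, which divides at most 240 staff further. A reader who relies on section 9.2 would expect clearly tighter estimates than the design can give.

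**Working it through.** **Inputs.** 16 clinics, ICC 0.05, SD 0.5 and 2.0, stated total widths 0.09 and 0.35 (section 9.2). Staff: at most 15 × 16 = 240 per wave (section 6.1). Patients: at least 35 × 16 = 560 (section 8), at most 3,000 (section 9.2).

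**Formulas.** Total 95% width = 2 × 1.96 × SD / √n_eff. With equal clinics of size m = n/16, n_eff = n / (1 + (m − 1) × 0.05).

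**Step 1: what the stated widths require.**
- SD 0.5: n_eff = (2 × 1.96 × 0.5 / 0.09)² ≈ 474 (426 to 532 allowing for rounding of 0.09).
- SD 2.0: n_eff = (2 × 1.96 × 2.0 / 0.35)² ≈ 502 (488 to 516 allowing for rounding of 0.35).

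**Step 2: can the plan's figures be reproduced?** As n grows, n_eff approaches 16 / 0.05 = 320, which is below both requirements. So no number of patients reproduces the pair as total widths under the stated assumptions. Ignoring clustering, 560 patients give 0.083 and 0.331; using a t quantile on 15 degrees of freedom instead gives 0.090 and 0.360. Neither gives both figures.

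**Step 3: staff and patients at one wave.**

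| Group | n | Design effect | n_eff | Width, SD 0.5 | Width, SD 2.0 |
|---|---|---|---|---|---|
| Stated in 9.2 | not given | not given | 474 / 502 implied | 0.09 | 0.35 |
| Staff, no clustering | 240 | 1 | 240 | 0.127 | 0.506 |
| Staff, ICC 0.05 | 240 | 1 + 14 × 0.05 = 1.70 | 141.2 | 0.165 | 0.660 |
| Staff, ICC 0.05, 50% response (assumption) | 120 | 1 + 6.5 × 0.05 = 1.325 | 90.6 | 0.206 | 0.824 |
| Patients, ICC 0.05 | 560 | 1 + 34 × 0.05 = 2.70 | 207.4 | 0.136 | 0.544 |
| Patients, ICC 0.05 | 3,000 | 1 + 186.5 × 0.05 = 10.325 | 290.6 | 0.115 | 0.460 |
| Limit, ICC 0.05 | any | n/a | 320 | 0.110 | 0.438 |

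At SD 1.0, an intermediate value added here, the staff widths with ICC 0.05 are 0.330 at 240 respondents and 0.412 at 120.

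**Step 4: ratios to the stated widths (SD 0.5, SD 2.0).** Staff with no clustering: 1.41, 1.45. Staff with ICC 0.05: 1.83, 1.89. Staff at 50% response: 2.29, 2.35. Patients at 560: 1.51, 1.56. Patients at 3,000: 1.28, 1.31.

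**The case against.** **Section 9.2 is about patients.** The Likert widths are said to correspond to what precedes them, which concerns patients given the decision aid, and the section ends on the patient target. The figures point the same way: 5.3% at a proportion of 10% implies n_eff of about 492, which gives Likert widths of 0.088 and 0.353, close to the stated pair. This stands in part. The section applies the widths to staff only through its general wording, and a reader might infer that it makes a specific promise about staff precision. It does not. But its declared scope is all of quantitative Aim 2, and in section 9.4.2 it is the staff ratings that are expressly scored 1 to 5. On the patient-only reading, staff precision is missing and the widths still fail for patients.

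**The widths may be half-widths.** With 12 respondents per clinic and ICC 0.05 (n = 192, n_eff 124), half-widths are 0.088 and 0.352, which round to the stated pair. On that reading 240 staff would meet the figures (0.083 and 0.330 with ICC 0.05). But the section calls its width total, and 12 per clinic appears nowhere in the documents.

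**Staff are surveyed four times.** A mean pooled over 960 responses, with an assumed within-person correlation of 0.3 and no clustering by clinic, has n_eff = 960 / (1 + 3 × 0.3) = 505 and widths of 0.087 and 0.349. A reader might infer that the staff widths are unreachable in every sense; the documents support that only for a mean at one wave. The plan does not describe a pooled mean, however, and its hypothesis is about change over time.

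**The consequences are limited.** No sample size decision rests on the staff width, and reported intervals will come from the data through GEE with robust standard errors. This is correct, and it bounds the importance of the point.

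**Conclusion.** The point holds for the mean score at a single wave, with width read as total, as section 9.2 says.

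- For staff it does not depend on the ICC. Even with full response and no clustering, 240 respondents give intervals about 1.4 times as wide as stated; with ICC 0.05 they are 1.8 to 1.9 times as wide. Applying 0.05 to staff is an assumption, since section 9.2 does not tie its ICC to an outcome or a group.
- For patients it does depend on the ICC. Without clustering, 560 patients would do slightly better than stated. With the plan's own 16 clinics and ICC 0.05, the stated widths are out of reach at any enrolment. It would therefore be wrong to keep 0.09 and 0.35 as the patient figures.

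The clustered figures assume equal clinic sizes. The patient figures also assume that every patient answers; losses at 3 and 6 months would widen them.

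A reader might go further and infer that staff trajectories will be estimated with about twice the error promised. The documents do not support that number. Precision of change depends on the within-person correlation, which they do not give. Nor is the study invalidated: this is a misstated planning figure that should be corrected.

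**What to change.** Replace the Likert sentence in section 9.2 with separate figures for patients and staff, for example:

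> Total 95% CI widths for a mean score at one survey wave, assuming 16 clinics of equal size and an ICC of 0.05, are as follows. Patients: 0.14 (SD 0.5) and 0.54 (SD 2.0) with 560 respondents; 0.12 and 0.46 with 3,000. Clinic personnel: 0.17 (SD 0.5), 0.33 (SD 1.0) and 0.66 (SD 2.0) with 240 respondents and full response. If 50% of personnel respond, which is an assumption, the widths are 0.21, 0.41 and 0.82. These widths do not apply to change over time.

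State the formula beside the figures. List the staff-rated outcomes consistently as well: sections 4 and 9.4.2 name three, while sections 2.2, 6.1 and 8 add appropriateness and feasibility. The widths for proportions in section 9.2 need the same recalculation, because 5.3% at 10% and 8.1% at 40% imply n_eff of about 492 and 562, also above 320.

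The cost is a few sentences, with no change to design or data collection. The downside is that the stated precision becomes less favourable.

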6.3 Implementation Strategy Fidelity and Adaptation

Study investigators will develop and work with clinic personnel to apply the standardized and tailored implementation activities within the clinic setting. It is expected that strategies will be adapted to suit each clinic's unique context and circumstances. We therefore expect to implement 16 different approaches. We will capture and describe each unique approach and use these findings to inform key outcomes. The periodic check-ins for each site following the Education, Training, and Refresher Training standardized activities will allow study personnel to determine the extent to which the DA has been implemented within clinic flow and processes.

Patient participant study compliance will be measured by completion of all study assessments, including the three and six month follow-up and semi-structured in-depth phone interviews. We will also assess whether or not the patient views the DA at the first visit at baseline and/or requests an electronic or paper copy of the DA (Aim 2).

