9.4.6 Sub-Group Analyses

We are planning the following subgroup analyses, if enough data are available. The analysis approaches are described above.

- Clinics with vs. without prior experience with DA,
- Setting, private vs. academic,
- Location, urban vs. suburban,
- Type of clinic, general rheumatology clinic vs. lupus clinic vs. rheumatology/renal hybrid clinic,
- By the language of decision-aid used English vs. Spanish,
- Patient characteristics including the biological variables (age group, sex, race/ethnicity), and
- The proportion of patients with Medicaid/Medicare vs. private insurance
- By presence of renal disease
- By level of education
- By insurance mix (>30% private)

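### Section 9.2 says 16 clinics can comprehensively assess strategy-by-context interaction and settle generalizability; the design supports only exploration of the combinations that occur

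*Combined protocol and SAP*

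**What the plan says.** Section 9.2 states that "A minimum number of proposed sites (n=16) are needed" and gives the purpose: these sites "are needed to comprehensively assess how different implementation strategies are influenced by and interact with different contextual conditions". The conditions are listed as "different geographic areas, clinic type, and patient diversity". The sentence then draws an inference: "and thus, determine the generalizability of the study findings". This is the only reason that 9.2 gives for the number of clinics.

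Other sections describe what the clinics will provide:

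- Section 6.1 lets each site choose clinic-targeted activities, patient-targeted activities or both, on top of standardized activities given to all 16 clinics.
- Section 6.3 expects adaptation to each clinic: "We therefore expect to implement 16 different approaches".
- Section 9.1 groups sites by strategy after completion and adds a group covariate to the GEE models, to see whether trajectories differ by strategy. Comparisons by clinic characteristics are optional and are run separately.
- Sections 9.1 and 9.4.2 assign clinic-level strategy effectiveness to fsQCA.
- Section 9.4.6 lists, if data suffice, "Setting, private vs. academic", "Location, urban vs. suburban" and "Type of clinic, general rheumatology clinic vs. lupus clinic vs. rheumatology/renal hybrid clinic".
- Section 9.4.7 hopes for two distinguishable strategy groups and provides fallback groupings if they do not emerge.

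**The concern.** A sample-size section should state what the sample can show. Here the number of clinics rests on a claim about interaction across three contextual factors, yet 9.2 gives no count of combinations, no interaction precision and no derivation of 16. Its figures are interval widths for one overall proportion or mean.

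The claim matters because it sets what may be concluded. If few clinics share a strategy and a context, failure to see a difference between contexts is weak evidence. A reader who relies on 9.2 could still take it as a sign that the strategies work everywhere, and carry that into the implementation manual planned under Aim 3. Recruiting on to 3,000 patients does not cure this, because the scarce unit is the clinic.

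**Working it through.** **The plan's own figures.** There is no calculation of 16 to reproduce. The interval widths in 9.2 (5.3%, 8.1%, 0.09 and 0.35) concern single overall estimates and cannot support an interaction claim. They also do not follow from the stated ICC of 0.05. With 16 clinics the effective sample size cannot exceed 16/0.05 = 320, so the 95% widths cannot fall below 2 × 1.96 × sqrt(0.09/320) = 6.6%, 2 × 1.96 × sqrt(0.24/320) = 10.7%, and 0.11 and 0.44 for SDs of 0.5 and 2.0. That is a separate matter and is not needed here.

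**Counting combinations.** Section 9.2 defines no levels, so these are taken as follows:

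- strategy groups: 2 (9.4.7), or 3 if sites split into clinic-targeted, patient-targeted and both (6.1);
- geography: 2, using urban and suburban from 9.4.6 as a coarse stand-in;
- clinic type: 2 (5.1 and 6.2 name general rheumatology and lupus clinics) or 3 (9.4.6);
- patient diversity: 2, an assumption and the smallest possible number.

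Combinations C = product of the levels. If clinics fell at random and evenly over C combinations (an assumption for scale only), the expected number occupied is C × (1 − (1 − 1/C)^16).

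| Strategy × geography × type × diversity | Combinations | Clinics per combination | Expected occupied |
|---|---|---|---|
| 2 × 2 × 2 × 2 | 16 | 1.0 | 10.3 |
| 2 × 2 × 3 × 2 | 24 | 0.67 | 11.9 |
| 3 × 2 × 3 × 2 | 36 | 0.44 | 13.1 |

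In the coarsest grid, filling every combination requires exactly one clinic in each. Under random placement that has probability 16!/16^16, about 1 in a million. With 24 combinations at least 24 − 16 = 8 must be empty. Adding private versus academic setting would double each count.

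**What the models contain.** The GEE models in 9.1 carry a strategy-group covariate. Contextual comparisons are separate. No term crosses strategy with context, so the models as written do not estimate the interaction that 9.2 gives as the reason for 16 clinics.

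**Illustrative detectable differences.** Inputs: ICC 0.05 (9.2), significance level 0.05 (9.4.4, taken as two-sided), 35 patients per clinic (section 8) or 3,000/16 = 187.5, and an assumed 80% power. The outcome is measured once and clinics are of equal size.

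- Variance of a clinic mean, in SD² units: v = 0.05 + 0.95/m. This is 0.0771 at m = 35, 0.0551 at m = 187.5 and 0.05 with unlimited patients.
- Detectable difference = (t0.975 + t0.80) × sqrt(v × sum of 1/n over groups). The multiplier is 3.013 for two groups (14 df) and 3.051 for a 2x2 interaction (12 df).

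| Comparison | Sum of 1/n | m = 35 | m = 187.5 |
|---|---|---|---|
| Two strategy groups, 8/8 | 0.25 | 0.42 SD | 0.35 SD |
| Two strategy groups, 4/12 | 0.333 | 0.48 SD | 0.41 SD |
| 2x2 interaction, 4/4/4/4 | 1 | 0.85 SD | 0.72 SD |
| 2x2 interaction, 6/6/2/2 | 1.333 | 0.98 SD | 0.83 SD |

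With unlimited patients the balanced values are still 0.34 and 0.68 SD.

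The Aim 2 analyses concern change over time, and the plan gives neither a within-patient correlation nor an ICC for change. Assuming a correlation of 0.3 to 0.7 and an ICC of change of 0.01 to 0.05, the balanced values in baseline SD units run from about 0.14 to 0.50 for strategy and 0.29 to 1.00 for the interaction. The table is therefore for scale only.

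**The case against.** The strongest reply is that this is declared in 5.1 to be an observational case study, and that fsQCA is the planned tool for asking which conditions, alone or together, are necessary or sufficient for an outcome. It is meant for small numbers of cases and tolerates empty combinations, so judging the study as a powered factorial experiment is unfair. Much of this stands. The plan does have a route for examining strategy and context together. But fsQCA has no outcome data for combinations that do not occur, so it supports exploration, not a comprehensive assessment or a finding on generalizability. Section 9.2 also places the claim in a power analysis for the quantitative part of Aim 2.

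Three stronger readings are tempting, and the documents do not support them:

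- From 6.3 a reader might infer that each strategy is seen in one clinic only and is fully confounded with it. The 16 approaches are adaptations of standardized activities given to every clinic and of a common menu (6.1). Components recur across clinics, and sites are to be grouped.
- A reader might infer that there must be fewer clinics than combinations. That depends on the three clinic types in 9.4.6. With the two in 5.1 and 6.2 the coarsest count is a tie at 16.
- A reader might treat 0.35 to 0.42 SD and 0.72 to 0.85 SD as the study's detectable differences. They are best-case, balanced, single-time values. Sites choose their activities and enrolment is competitive, so balance is not controlled, and the analyses target change.

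It is also fair to say that no interaction test is planned, so misreading a null test is a risk, not a written intention. The wording of 9.2 is what invites it.

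**Conclusion.** The point holds, limited to the claim in 9.2. Sixteen clinics that choose their own activities and are grouped afterwards cannot comprehensively assess how strategies interact with three contextual factors, nor determine generalizability. On the coarsest count there is on average one clinic per combination, and fewer on the plan's own three clinic types. Some combinations will very likely be empty, and no model term addresses the interaction.

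The conclusion does not depend on whether the count is 16 or 24, since both leave little or no replication. It rests on at least two levels per factor, where two levels of diversity is an assumption. The detectable differences show scale only. The documents do not show that the strategy comparison is worthless or that fsQCA is unsuitable.

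**What to change.** In 9.2, replace the sentence that justifies the number of clinics with a statement that:

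- assessment of strategy by context is exploratory, done through fsQCA and through by-group comparisons of one contextual factor at a time;
- the number of strategy-context combinations actually occupied will be reported (the levels used for each factor must then be stated);
- absence of an observed difference or interaction will not be read as evidence of generalizability.

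If detectable differences are quoted, label them illustrative best-case values for a single-time outcome, with ICC 0.05, equal clinics and assumed 80% power: about 0.35 to 0.42 SD for an 8/8 strategy split and 0.72 to 0.85 SD for a balanced 2x2 interaction. Add that imbalance makes them larger (0.41 to 0.48 SD for 4/12; 0.83 to 0.98 SD for 6/6/2/2) and that they do not apply directly to change scores.

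No extra clinics, patients or data collection are needed. The cost is a less favourable statement of what 16 clinics can show.
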